3.4. Subgroup Analysis Sets

3.4.1. Age Strata

Selected efficacy endpoints including CAEs (primary), pre-bronchodilator FEV₁, AQLQ+12, ACQ-6, and blood eosinophils will be analyzed separately for patients aged 12 to <18 years and ≥18 years. Age strata will be defined based on the age recorded in the clinical database.

3.4.2. Eosinophil Strata

Selected efficacy endpoints including CAEs (primary), pre-bronchodilator FEV₁, AQLQ+12, ACQ-6, and blood eosinophils will be analyzed separately for patients with baseline blood eosinophil levels 300/μL to <400/μL and ≥400/μL. Eosinophil strata will be defined based on the baseline blood eosinophil level recorded in the clinical database.

3.4.4. Asthma Background Medication

Patient classifications based on Global Initiative for Asthma (GINA) guidelines ([GINA 2015](#)) will be derived. Selected efficacy endpoints including CAEs and pre-bronchodilator FEV₁ will be examined for the following medication classes taken at baseline. Medications at baseline will be defined as those taken at the time of randomization.

- **GINA 4 – ICS/LABA+ (Yes, No)**
Note: “Yes” is defined as patients taking ICS (medium or high-dose); and LABA or leukotriene or xanthine as a second controller; and no OCS use
 - ICS/LABA (Yes, No)
Note: “Yes” is defined as patients taking ICS (medium or high-dose); and LABA as a second controller; and no OCS use
 - High-dose ICS/LABA (Yes, No)
Note: “Yes” is defined as patients taking ICS (high-dose); and LABA as a second controller; and no OCS use
 - Medium-dose ICS/LABA (Yes, No)
Note: “Yes” is defined as patients taking ICS (medium-dose); and LABA as a second controller; and no OCS use

- **GINA 5** – OCS (Yes, No)
Note: “Yes” is defined as patients taking OCS

3.4.5. Other Subgroups

Selected efficacy endpoints including CAEs (primary), pre-bronchodilator FEV₁, AQLQ+12, ACQ-6, and blood eosinophils will also be examined for the following demographic subgroups:

- Gender (Male, Female)
- Race (White, Black, Asian, Other; Black, non-Black)
- Region (North America, Eastern Europe, Western Europe, Latin America, Asia/Pacific, Middle East/Africa; US, non-US)
- Phadiatop result (Positive, Negative)
- Age of asthma onset (<40, ≥40 years)
- BMI (<30, ≥30 kg/m²)
- ADA status (Positive, Negative) – for reslizumab-treated patients only

4. GENERAL ISSUES FOR DATA ANALYSIS

4.1. General

Descriptive statistics for continuous variables include number of patients (n), mean, standard deviation (SD), standard error (SE) of the mean, median, minimum, and maximum. If inferential statistics are computed, the least square (LS) mean and standard error of the LS mean will be included. Descriptive statistics for categorical variables include patient counts and percentages.

4.2. Specification of Baseline Values

4.2.1. Diary

Baseline for diary variables (eg, PEF, total asthma symptom score, total reliever use) will be derived as the average of the run-in values over the 7 days preceding baseline/DoR (see [Table 3](#) for the definition of analysis days for diary data). At least 4 out of the 7 expected measurements need to be recorded for each diary variable; otherwise the baseline value for that variable will be treated as missing.

4.2.2. Lung Function

The baseline value for lung function variables (eg, pre-bronchodilator FEV₁, FVC, FEF_{25%-75%}) will be the last observed pre-bronchodilator value prior to the first dose of study drug. Baseline for post-bronchodilator FEV₁ will be the last observed post-bronchodilator value prior to the first dose of study drug.

4.2.3. Patient Reported Outcomes

The baseline value for patient reported variables (eg, ACQ-6, AQLQ +12, SGRQ, ████████) will be the last observed value prior to the first dose of study drug.

4.2.4. Biomarkers

The baseline value for blood eosinophil levels will be the maximum value of the observed assessments from the screening visit to baseline/DoR (inclusive).

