### **3.9. Randomization and Blinding**

This is a randomized, double-blind, placebo-controlled study. Patients who meet all inclusion criteria and none of the exclusion criteria will be randomly assigned to receive reslizumab 110 mg sc or matching placebo (approximately 225 patients per treatment group) in a 1:1 ratio. Patients and investigators will remain blinded to treatment assignment during the study. Randomization will be stratified by age (12 to <18 and  $\geq 18$  years), and blood eosinophil levels at screening (300/ $\mu\text{L}$  to <400/ $\mu\text{L}$  and  $\geq 400/\mu\text{L}$ ). This system is used to ensure a balance across treatment groups. The goal is to recruit a maximum of 30% of the patients (60 patients per treatment group) with eosinophil levels of 300/ $\mu\text{L}$  to <400/ $\mu\text{L}$ .

The randomization list and treatment will be assigned to the relevant treatment groups through a qualified contract research organization (CRO), eg, via Interactive Voice Response System (IVRS)/ Interactive Web Response System (IWRS). The generation of the medication list and management of the IRT system will be done by a qualified CRO under the oversight of Teva's Clinical Supply Chain.

The sponsor's clinical personnel involved in the study will also be blinded to the study drug identity after the run-in period until the database is locked for analysis and the treatment assignment is revealed, with the exception of the bioanalytical group who will not be blinded to facilitate PK and ADA sample analysis. Eosinophils and monocytes will be redacted from the post-baseline differential cell count reports to avoid the possibility of unblinding patients.

Each patient will receive either one 1.0-mL sc injection containing 110 mg of reslizumab or one 1.0-mL sc injection containing sterile placebo solution on each dosing day. Both reslizumab and placebo will be provided as clear solutions essentially free of particulate matter.

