### **9.5.6. Planned Method of Analysis**

The ITT analysis set (see Section 9.2.1) will be used for all efficacy analyses. Summaries will be presented by treatment group. The per-protocol analysis set will be used as sensitivity analysis for the primary analysis.

The baseline for diary variables will be the average of the run-in values over the 7 days preceding baseline/DoR. The baseline for clinic visit variables will be the last observed value before the first dose of study drug. The baseline for eosinophils levels analysis will be screening value.

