3. Eosinophil levels at baseline categories. Patients with blood eosinophil levels at baseline of  $300/\mu\text{L}$  to  $<400/\mu\text{L}$  and  $\geq 400/\mu\text{L}$  will be analyzed separately.

Additional subgroup analyses may be performed. These will be described and detailed in the statistical analysis plan.

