6.2.3. Sensitivity Analyses for the Primary Variable

The following list of sensitivity analyses are pre-specified for this study, with an aim toward assessing the robustness of the primary efficacy results:

- The primary analysis with offset variable calculated as the logarithm of follow-up duration (ie, not excluding the summed duration of exacerbations).
- The primary analysis with control variables for age and blood eosinophil categories based on data recorded in the IRT (as randomized). This analysis will only be

performed if the number of discrepancies between data recorded in the IRT and the clinical database are sufficiently large (eg, 5% of total population).

- **On-treatment:** analysis of the primary endpoint including exacerbations during the treatment period (ie, observed until treatment completion or until withdrawal from treatment, excluding any exacerbations observed after withdrawing from treatment).
 - For patients who complete treatment, the treatment period will be defined from the first dose of study drug to the end of treatment (week 52) visit. For patients who prematurely discontinue treatment, the treatment period will be defined from the first dose of study drug to the last dose of study drug + 4 weeks.
- **Per-protocol:** on-treatment analysis of the primary endpoint including exacerbations during the treatment period (ie, observed until treatment completion or until withdrawal from treatment, excluding any exacerbations observed after withdrawing from treatment), based on the PP analysis set.
- **“Tipping point” multiple imputation:** analysis of the primary endpoint to assess deviations from missing at random (MAR). The details regarding this analysis are provided in [Appendix B](#).

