6.2.5. Subgroup Analysis for the Primary Variable

The primary efficacy variable will additionally be examined for the subgroups defined in Section 3.4. The analysis will be similar to the on-treatment analysis described for the primary endpoint (Section 6.2.3). An interaction p-value will be derived from a separate NB model including additional terms for subgroup and treatment by subgroup interaction. Subgroup analyses for the primary efficacy variable will be presented graphically using forest plots.

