8.2. Pharmacodynamic Analysis

8.2.1. Target Biomarker (Blood Eosinophil Counts)

The target biomarker endpoints are the blood eosinophil counts at baseline/DoR; weeks 2, 4, 8, 12, 16, 32, 52 or early withdrawal; and the follow-up visit (approximately week 64).

Summary statistics of actual values, change from baseline, and percent change from baseline to each scheduled visit will be provided by treatment group, using the ITT analysis set. A line graph will be provided summarizing the mean blood eosinophil counts at each visit.

Blood eosinophils will additionally be examined for selected subgroups defined in Section 3.4. As described above, the analysis of eosinophils by subgroups will be summarized descriptively.

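### SAP 4.2.4 takes the highest pre-dose eosinophil count as baseline where the protocol uses the screening value, so the eosinophil subgroups differ from the randomised strata and within-arm falls look larger

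*SAP*

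**What the plan says.** **Baseline.** Protocol 9.5.6, and the synopsis in the same words: "The baseline for eosinophils levels analysis will be screening value". SAP 4.2.4: "The baseline value for blood eosinophil levels will be the maximum value of the observed assessments from the screening visit to baseline/DoR (inclusive".

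**Randomisation.** Protocol 3.9 and SAP 2.4 stratify by age "and blood eosinophil levels at screening", with cut points at 300 to <400 and ≥400/µL. Enrolment to the lower stratum is capped.

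**Subgroups.** Protocol 9.5.6.1 plans separate analyses: "Patients with blood eosinophil levels at baseline of" 300 to <400 and ≥400/µL. With the protocol's own baseline these are the screening strata. SAP 3.4.2: "Eosinophil strata will be defined based on the baseline blood eosinophil level recorded in the clinical database". Read with 4.2.4, that level is the maximum. SAP 6.2.5 adds an interaction test from a model "including additional terms for subgroup and treatment by subgroup interaction".

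**Biomarker tables.** SAP 8.2.1: "Summary statistics of actual values, change from baseline, and percent change from baseline to each scheduled visit will be provided by treatment group".

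**Record of the change.** SAP Section 10 declares that nothing departs from the analyses in protocol Amendment 04. Table 8, in the same section, shows the old and new text of 4.2.4 with a reason, as a change from the original SAP. The SAP preface says that the SAP governs where the two documents differ and that the study report will explain differences.

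**The concern.** The SAP governs, so the maximum would be used. Two things follow.

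First, the subgroup and interaction results would describe groups other than those stratified and capped at randomisation. The 300 to <400/µL group is the smaller one, and the shift only removes patients from it. The earlier intravenous evidence in protocol 1.3.2.2 defined eosinophilic asthma by a screening count of ≥400/µL, and a subgroup built on a maximum is not directly comparable with that.

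Second, change and percent change are measured from a value chosen because it is high, so a fall appears on placebo as well as on drug. A reader of Section 10 alone would not learn that the protocol's rule had been replaced.

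**Working it through.** The plan gives no figure of its own to reproduce here. The direction follows from the definitions; the size needs assumptions.

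**1. Direction.** Let S be the qualifying screening count, D the DoR count and F a later count. The SAP baseline is at least max(S, D), which is never below S.
- If S ≥ 400, the SAP baseline is ≥ 400, so nobody moves down.
- If 300 ≤ S < 400 and D ≥ 400, the patient is stratified low and analysed high.
- Mean fall from the maximum minus mean fall from screening = E[max(S, D)] − E[S], which is ≥ 0 in each arm.
- S and D are both pre-dose, so E[baseline] is the same in the two arms under any of the definitions. It cancels from the expected between-arm difference in absolute change.

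**2. Size (assumed inputs).** Counts are log-normal; median usual level 300, 380 or 500/µL; between-patient log-SD 0.5 or 0.6; within-patient log-SD 0.1, 0.2, 0.3 or 0.5; independent noise at screening, DoR and follow-up; entry on S ≥ 300; strata weighted 30/70. That is 3 × 2 × 4 = 24 scenarios, 1,000,000 simulated patients each.

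| Quantity | Range over scenarios |
|---|---|
| Low stratum moved up, p = P(D ≥ 400 given 300 ≤ S < 400) | 17-53% |
| p at within-patient log-SD 0.1 / 0.3 / 0.5 | 17-23% / 32-46% / 36-53% |
| Low subgroup as analysed, 0.30 × (1 − p) | 14-25% of patients |
| Untreated mean fall, maximum as baseline | 31-217 cells/µL |
| Untreated mean fall, screening as baseline | 1-97 cells/µL |
| Excess of maximum over screening, within scenario | 25-194 cells/µL |
| Untreated mean change, DoR as baseline | about 0 |

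The excess is taken scenario by scenario, so it is not the difference between the end points of the two ranges.

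**3. Second set of assumptions.** Median 300 or 400/µL with total log-SD 0.8 or 0.7, intraclass correlation 0.5-0.9, one repeat if the first screening count is below 300, and 60 of 225 per arm in the low stratum. Here 28-42% of the low stratum moves up: 60 × 0.28 ≈ 17 to 60 × 0.42 ≈ 25 patients per arm, or 0.267 × 0.28 = 7.5% to 0.267 × 0.42 ≈ 11% of all patients. The mean baseline is 11-19% above the screening value.

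**4. Whether the logged reason needs the DoR count.** Table 8 says the rule covers patients who reached the threshold before randomisation but not at the screening visit. Inclusion criterion e requires the threshold to be met before visit 2, and footnote e to protocol Table 2 allows one repeat during screening. The qualifying value is therefore always a screening count, and DoR adds nothing to that purpose.

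**5. Whether an existing check covers this.** SAP 6.2.3 plans "The primary analysis with control variables for age and blood eosinophil categories based on data recorded in the IRT (as randomized", to be run if discrepancies are large (5% is the example). It concerns the primary model. Nothing similar is planned for the subgroup analyses.

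**The case against.** **The plan may change analyses, and this edit is visible.** Protocol Section 9 lets the SAP change analyses, 9.12 lets deviations be described in the SAP or the study report, and Table 8 shows old rule, new rule and reason. This stands: a reader might infer concealment, and the documents do not support that. What remains is that the opening statement of Section 10 is untrue for this item, because Table 8 compares the edit with the earlier SAP and not with the protocol.

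**The protocol is not uniform.** Section 5.1 can be read as stratifying at baseline/DoR, and 2.3.4 lists a count at baseline/DoR. True, but neither is a maximum.

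**The placebo fall is not all due to the maximum.** A reader might attribute it entirely to SAP 4.2.4. Entry requires S ≥ 300, so the screening baseline also carries regression to the mean (1-97 cells/µL above). In the scenario with median 300 and log-SDs 0.5/0.5, this selection accounts for about half of the fall seen with the maximum. Only the 25-194 excess belongs to the SAP's rule.

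**DoR is not plainly the better main baseline.** It removes the mean-change artefact, but it would itself depart from protocol 9.5.6. As a denominator it also gives an untreated mean percent change of exp(w²) − 1, with w the within-patient log-SD: +1% at w = 0.1 and +28% at w = 0.5.

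**The maximum does not favour the drug.** If treatment multiplies the later count by r < 1, the between-arm contrast in mean percent change is 100 × (1 − r) × E[F/baseline]. A larger baseline shrinks it, so the bias in that contrast runs against reslizumab.

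**Conclusion.** The concern holds, with limited reach. The protocol and SAP rules conflict, the SAP rule would be applied, and its effect has a certain direction: patients move only from the low to the high subgroup, and within-arm falls are larger in both arms. The size rests on assumed variability. About 17-53% of the low stratum moves (28-42% under the second set of assumptions), and the fall exceeds that from the protocol baseline by about 25-194 cells/µL.

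The expected between-arm difference in absolute change and the actual values at each visit are untouched. Subgroup membership is fixed before dosing, so comparisons within subgroups remain randomised. The affected analyses are exploratory or descriptive and carry no multiplicity control. The harm is to interpretation.

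A reader might go further in either direction on the primary test, and the text supports neither. SAP 6.2.2 refers to the categories in Section 2.4, which are screening categories, so the natural reading is that the test is unaffected. It also says they come from the clinical database and does not name the count. If the maximum were used there, the 7.5-11% discordance above would exceed the 5% example that triggers the sensitivity analysis in 6.2.3.

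**What to change.** 1. SAP 3.4.2: define the eosinophil subgroups by the qualifying screening count used to stratify randomisation.
2. SAP 4.2.4: restore the protocol's screening value for change from baseline, defined as the qualifying count when the test was repeated. Add the DoR count as a sensitivity summary.
3. SAP 6.2.2: state that the eosinophil covariate uses the screening count and not the 4.2.4 maximum.
4. SAP Section 10: correct the opening statement so that it lists any remaining departure from protocol 9.5.6.

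The cost is wording in four places and one extra descriptive summary. Screening and DoR counts are both already collected under protocol Table 2, so no new data are needed. Under the assumptions above, reported within-arm falls become smaller by about 25-194 cells/µL. The expected between-arm difference in absolute change stays the same.

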4.2.5. Safety

The baseline value for all visit-based safety assessments (eg, laboratory, vital signs) will be the last observed value prior to the first dose of study drug.

4.3. Multiple Comparisons and Multiplicity

A fixed sequence multiple testing procedure will be implemented to test the primary and secondary variables while controlling the overall type I error rate at 0.05. If the resulting two-sided p-value from the primary comparison is ≤ 0.05 , then the next comparison of interest (first secondary variable) will be interpreted inferentially at 0.05. This process continues through the secondary variables until either all comparisons of interest are interpreted inferentially, or until the point at which the resulting two-sided p-value for a comparison of interest is > 0.05 . At the

point where $p > 0.05$, no further comparisons will be interpreted inferentially. The hierarchy of endpoints is as defined in Section 6.3.1.

No multiplicity adjustments will be made for other efficacy and exploratory analyses.

4.4. Handling Withdrawals and Missing Data

The primary analysis will include multiple imputations for missing data as detailed in Section 6.2.2 and Appendix A. For all other variables, only the observed data from the patients will be used in the statistical analyses (ie, there is no plan to estimate missing data).

4.5. Study Days and Visit Windows

Study days will be numbered relative to the first day of study drug administration. The start of treatment (day 1) is defined as the date on which a patient takes the first dose of study drug, as recorded on the study drug diary. Days will be numbered relative to study start (ie, ..., -2, -1, 1, 2, ...) with day 1 being the start of study drug and day -1 being the day before the start of study drug).

For safety-by-visit summaries, if there are multiple assessments at a post-baseline visit then the last non-missing assessment at that visit will be used for the analysis. This includes assessments at the scheduled and unscheduled visits.

‘Endpoint’ for safety analyses and summaries is the time point when the last observation was obtained during the treatment period. For patients who completed treatment in this study, the treatment period will be defined from the first dose of study drug to the end of treatment (week 52) visit. For patients who prematurely discontinue treatment, the treatment period will be defined from the first dose of study drug to the last dose of study drug + 4 weeks.

For efficacy-by-visit summaries, only the assessments at the scheduled visit will be summarized. The assessments at unscheduled visits will be listed. For the purpose of the efficacy analysis, assessments collected at an early termination visit will be considered as the next scheduled visit for that assessment if at least 3 but no more than 5 weeks elapsed since the date of the last medication intake.

Efficacy-by visit summaries will be presented on-treatment. In this context, ‘endpoint’ will be defined as the last observation obtained at a scheduled or qualified early termination visit during the treatment period. For patients who completed treatment in this study, the treatment period will be defined from the first dose of study drug to the end of treatment (week 52) visit. For patients who prematurely discontinue treatment, the treatment period will be defined from the first dose of study drug to the last dose of study drug + 4 weeks.

For selected variables, additional sensitivity analyses may be presented utilizing all data collected over the entire course of the study including data collected after withdrawal for patients who prematurely discontinue from treatment. In this context, ‘endpoint’ will be defined as the last observation obtained at any post-baseline scheduled or qualified early termination visit.

For summaries of diary data (eg, rescue medication use, asthma symptom score), the day used for analysis will consist of the evening assessment for the day and the morning assessment for the following day, as illustrated in Table 3. Weekly average data will be generated using 7-day windows derived based on these analysis days.

Table 3: Definition of Analysis Days for Diary Data

Study Period	Diary Day	Study Day ^a	Time Point	
Baseline	Day -7	-7	PM	
		-6	AM	
	Day -6	-6	PM	
		-5	AM	
	Day -5	-5	PM	
		-4	AM	
	Day -4	-4	PM	
		-3	AM	
	Day -3	-3	PM	
		-2	AM	
	Day -2	-2	PM	
		-1	AM	
	Day -1	-1	PM	
		1 (pre-dose)	AM	
	Treatment	Day 1	1	PM
			2	AM
Day 2		2	PM	
		3	AM	
Day 3		3	PM	
		4	AM	
...		..	PM	
		..	AM	
Day 364		364	PM	
		365	AM	

^a Study Day 1 denotes the first dose of study drug; Study Day -1 is the day prior to the first dose of study drug.

